surgery⁴. Recently, there has been increasing interest in the effectiveness of pain control with the use of quadratus lumborum blocks after THA . Currently, case reports have established a precedent regarding the efficacy of the QLB for THA^{5,6,10} in providing superior analgesia and decreasing verbal numerical pain scores, but randomized trials are still lacking. The goal of this study is to compare verbal numerical pain scores, post-operative pain medication (opioid) consumption, physical therapy scores, and patient satisfaction in patients that receive QLB versus no peripheral nerve blockade in patients undergoing THA. The results of this study have the potential to change the standard of care for patients undergoing THA.

b. Describe how outcomes will be measured for this protocol.

The primary end points are as follows:

1. Pain scores (numerical) will be obtained at immediate post op, 24 hours and 48 hours after surgery
2. Pain medication (opioid) use intraoperatively, as well as at 24 hours and 48 hours postoperatively
3. Physical therapist assessment of independence in mobility and transfers
4. Distance ambulated at 24 hours and 48 hours after surgery.

15. Background - in nontechnical, lay language

Summarize in 2-3 paragraphs past experimental and/or clinical findings leading to the design of this protocol. Include any relevant past or current research by the PI. For drug and device studies, summarize the previous results (i.e., Phase I/II or III studies).

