Currently, regional anesthesia techniques for total hip arthroplasty are limited. Fascia iliaca blocks (nerve blocks between the muscles of the hips) have been employed to provide analgesia for hip surgeries with blockade of the femoral, lateral femoral cutaneous, and obturator nerves via injection of local anesthetic in the iliacus fascia. In addition, lumbar plexus blocks have also been employed for post-operative analgesia, but the complexity of the block is high, and complications including epidural anesthesia are not infrequent. The quadratus lumborum block (QLB) is an abdominal truncal block in which local anesthetic is deposited into the thoracolumbar fascia (area between the muscle) or the quadratus lumborum muscle itself with the goal of providing analgesia to the ipsilateral T6 – L1 sensory dermatomes. It has already been demonstrated to provide effective post-operative analgesia for certain abdominal and pelvic surgeries⁷, but its use in total hip arthroplasty is limited to case reports.

The block is accomplished by locating the quadratus lumborum muscle, using a ultrasound probe. Local anesthetic is then injected. Cadaveric studies⁸ have demonstrated dye spread to the lumbar nerve roots and nerves within the transversus abdominis plane (TAP). Carney et al⁹ described a “posterior TAP” block, now known to be synonymous with QLB, that demonstrated contrast spread to the thoracic paravertebral space from T5-L1. Case reports have described analgesia in the corresponding sensory dermatomes after QLB⁴, and have demonstrated efficacy in patient undergoing THA^{5,6,10}. The QLB block has potential to cover lateral femoral cutaneous nerve, femoral nerve, obturator nerve and portions of lumbar plexus.

This study has been designed to investigate the efficacy of the QLB in providing post-operative pain control patients undergoing THA. Previous trials have demonstrated the effectiveness of the block for abdominal and pelvic surgeries, and case reports have shown its applicability in hip arthroplasty. In this randomized, controlled study we aim to compare QLB (block group) with control (control group) in patients undergoing THA with regard to verbal numeric pain scores (to be obtained when patient arrives to PACU & at discharge from PACU, then at 24 and 48 hours after surgery). The duration of analgesia, time to first opioid medication, physical therapy evaluations, time to discharge, and patient satisfaction scores will also be obtained.

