General Data Analysis Plan: All demographic and clinical variables with continuous measures will be expressed as means and standard deviations; categorical factors will be expressed as proportions. For non-normal data, the medians and inter quartile ranges will be displayed. The distribution of the continuous factors will be examined using the Kolmogorov-Smirnov test. For data that are normally distributed, the one-way ANOVA and Student's t-test will be used to compare groups of data. For data that are not normally distributed, the Kruskal-Wallis and Mann-Whitney tests will be used for comparisons. Chi-square and Fisher's exact tests will be used to analyze categorical data. For all comparisons, a value of $p < 0.05$ will be considered statistically significant.

Primary Outcome Analysis: Statistical analyses will be performed using SAS for Windows, version 9.2. Student's t-test will be used to compare post-operative pain scores for investigational and control subjects. Linear regression will be also be used to test the relationship between pain scores and regional anesthetic technique, while controlling for relevant clinical and demographic variables. Distance of first ambulation will be analyzed using Cox proportional-hazards model. Student's t-test will be used to compare patient and surgeon satisfaction.

Statistical Power and Sample Size Estimates : Sample size (50 each group) was determined using a Cohen's d table assuming a mean pain VAS score of 8 (SD = 3) on a scale of 0-10 for control subjects. A difference of VAS score of 3 between two study groups will be clinically relevant. A sample of 100 participants (50 patients per group) will have approximately 95% power to detect a reduction in pain score difference of 3 with significance level alpha of 0.05. We will perform an interim analysis after 50 patients have completed the study (25 patients in each group).

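### Four unranked primary end points, every comparison tested at p<0.05, and no stated pain time point or rule for success

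*Combined protocol and SAP*

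**What the plan says.** Item 14.b introduces its list with "The primary end points are as follows". Four entries follow:

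1. pain scores immediately after surgery, at 24 hours and at 48 hours;
2. opioid use, given as "Pain medication (opioid) use intraoperatively, as well as at 24 hours and 48 hours postoperatively";
3. the physical therapist's assessment of independence;
4. distance walked at 24 and 48 hours.

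Nothing ranks them. Item 15 gives four pain times instead of three: "to be obtained when patient arrives to PACU & at discharge from PACU, then at 24 and 48 hours after surgery".

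The General Data Analysis Plan states: "For all comparisons, a value of $p < 0.05$ will be considered statistically significant". It also sends non-normal data to rank tests, after a Kolmogorov-Smirnov check.

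The Primary Outcome Analysis paragraph names Student's t-test for pain. It adds a linear regression with covariates that are described only as relevant, a Cox model for the distance of first ambulation, and a t-test for patient and surgeon satisfaction.

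The sample size paragraph is about pain only and names no time: 50 patients per group "will have approximately 95% power to detect a reduction in pain score difference of 3". It also announces an interim analysis after 50 patients.

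**The concern.** A primary end point fixes in advance which result decides whether the trial succeeded. Here four end points carry that label, one of them at three or four times, and the only decision rule is p<0.05 for each comparison. The plan does not say whether one success is enough or all are needed.

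Taking pain as the lead does not close the gap, because the time at which pain decides is still open. The investigators could report as primary whichever time or end point reached 0.05 and correctly cite the protocol for it. Item 14.a says the results could change the standard of care, so the primary claim should be fixed beforehand.

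The analysis paragraph does not settle the matter either. It brings in satisfaction, which Item 14.b does not list. It uses first-ambulation distance where Item 14.b has distance at two fixed times. It assigns no specific analysis to opioid use or the physical therapist assessment, two of the four listed primaries.

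**Working it through.** **The plan's own figure.** Inputs from the sample size paragraph: difference 3, SD 3, 50 per group, alpha 0.05 (taken as two-sided, since sidedness is not stated).

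- Standardised difference: d = 3/3 = 1. Noncentrality: d × √(n/2) = √25 = 5, with 98 degrees of freedom.
- Power by the noncentral t distribution is 99.9%, so the stated figure of about 95% is not reproduced. With 25 per group the same formula gives 93.4%. That mismatch is a separate matter; here it only shows that there is power to spare for pain.

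**The two outcome lists side by side.**

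| Outcome | Item 14.b | Primary Outcome Analysis |
|---|---|---|
| Pain | yes, three times | yes, no time named |
| Opioid use | yes, three periods | no specific analysis |
| Physical therapist assessment | yes, no time named | no specific analysis |
| Distance | 24 and 48 hours | first ambulation |
| Patient and surgeon satisfaction | not listed | yes |

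**False-positive rate if any one success counts.** Take k two-sided tests at 0.05 with no true effect.

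- Independent tests: 1 − 0.95^k. For k = 3 this is 1 − 0.8574 = 14.3%; for k = 4 it is 1 − 0.8145 = 18.5%.
- Equally correlated tests with correlation ρ: 1 − ∫ [Φ((c − √ρ·u)/√(1−ρ)) − Φ((−c − √ρ·u)/√(1−ρ))]^k φ(u) du, with c = 1.96.

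The documents give no correlations, so a range is shown:

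| Assumed ρ | 0 | 0.3 | 0.5 | 0.7 | 0.8 | 0.9 |
|---|---|---|---|---|---|---|
| Three pain times (k = 3) | 14.3% | 13.6% | 12.5% | 10.9% | 9.8% | 8.4% |
| Four end points, one test each (k = 4) | 18.5% | 17.4% | 15.6% | 13.0% | 11.4% | 9.4% |

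**If all end points must succeed.** The chance that every test is falsely positive cannot exceed the chance for any one of them, 5%. There is no inflation. Power for the joint claim becomes the concern, and it cannot be computed because no effect size is given for the other three end points.

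**Power for pain under a stricter threshold.** Holm's strictest step for four primaries is 0.05/4 = 0.0125. With noncentrality 5 and 98 degrees of freedom, power is 99.2%, against 99.9% at 0.05.

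**Cost to another continuous end point.** With 50 per group, the standardised difference detectable with 80% power rises from 0.57 at 0.05 to 0.68 at 0.0125.

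**The case against.** The best reply is that pain is plainly the lead. It comes first in Item 14.b and first in the Primary Outcome Analysis, it is the sole basis of the sample size, and Item 15 states the aim as pain control: "This study has been designed to investigate the efficacy of the QLB in providing post-operative pain control". This stands as far as it goes, and it would be too strong to say that the plan gives no indication of a lead. But an implied lead does not override an explicit list of four primaries, and none of these places picks a pain time.

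A reader might infer more than the documents support in several ways.

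- **No test is specified for pain.** The t-test is named outright, the regression is described as an additional analysis, and the normality check decides between t-test and rank test. Error rates that assume an analyst may pick the best of these describe departures from the written rule. What remains is narrower: the primary paragraph names the t-test without condition, the general rule is conditional, and the covariates are unlisted. Which result decides should be stated.
- **Nine or ten primary tests.** Counting every measurement in Item 14.b gives nine comparisons (3 + 3 + 1 + 2), or ten with the four pain times of Item 15. The statistical section does not schedule them all, so error rates on that count should carry no weight.
- **The lay summaries contradict the primary list.** Item 14.a says "The goal of this study is to compare verbal numerical pain scores, post-operative pain medication (opioid) consumption, physical therapy scores, and patient satisfaction", and Item 15 says "physical therapy evaluations, time to discharge, and patient satisfaction scores will also be obtained". Both items are lay summaries, and neither of these sentences defines primary end points. The conflict that matters is Item 14.b against the Primary Outcome Analysis.
- **The interim adds to this inflation.** Items 20.a and 20.c place interim results analysis within safety monitoring, and nothing says that it can support an efficacy claim. Its missing threshold is a separate issue.

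It is also fair that, if the assumed effect of 3 points is real, the pain result would very probably survive correction. The risk lies with a null or small effect.

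**Conclusion.** The concern holds. The plan has four unranked primary end points, one threshold of 0.05 for every comparison, no chosen pain time and no success rule, and its primary analysis paragraph does not match its primary list.

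If any one significant result counts, the nominal 5% becomes about 11-14% over three pain times and 13-17% over four end points at correlations of 0.3-0.7. At 0.9 it is still 8.4% and 9.4%. These figures rest on assumed equal correlations, two-sided tests and that reading of success. A reader might take the inflation as certain; the documents do not support that, because an all-must-succeed rule would produce none. The defect is that the plan does not say which rule applies.

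This should be corrected before the trial's results are examined, because a credible prespecified primary cannot be recovered afterwards.

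**What to change.** Before any outcome data are examined, including at the interim:

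- Name pain as the single primary end point, either at one time chosen by the sponsor or by one prestated repeated-measures test across the listed times. Reconcile the three times in Item 14.b with the four in Item 15.
- Name one deciding test, with its covariates listed if it is the regression. Make the other pain analyses sensitivity analyses.
- Make the other end points and times secondary, tested in a stated fixed order only if the primary succeeds.
- Alternatively, keep four primaries with one comparison each, under Holm's procedure and a written success rule.
- Use the same primary list in Item 14.b and the statistical section, give each listed end point an analysis, and move satisfaction out of the primary analysis paragraph.

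The cost is wording in the protocol and the statistical section, with no extra patients for pain. The downside is that the other end points become supportive or face a stricter threshold, and their power cannot be judged from the documents.

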16. Participants (Screening and Selection)

- a. How many participants are to be enrolled at UAB (if other sites relying on UAB IRB, list the number for each site)? **100**
If multi-site study, total number at all sites/institutions: **N/A**
- b. Describe the characteristics of anticipated or planned participants (if multiple groups, repeat list for each group).
Sex: **M,F**
Race/Ethnicity: **any**
Age: **>18 years**
Health status: **American Society of Anesthesiologist (ASA) Physical Status Score 1, II, or III**
- c. From what population(s) will the participants be derived? **All patients scheduled for total hip arthroplasty are scheduled in the preoperative assessment clinic days to weeks prior to their surgery. Study participants will be derived from this population.**

Describe your ability to obtain access to the proposed population that will allow recruitment of the necessary number of participants: **Before total hip arthroplasty, all patients report to the Highlands Preoperative assessment Clinic (HPAC) for standard of care preoperative assessment and examination and preoperative testing, tailored to patient comorbidities. This is not a service that will be billed additionally for study participants, as it is standard of care for all total hip arthroplasty patients, regardless of participation in the study. During this visit they will be given a “Patient Information Sheet,” describing the study. On the day of surgery, patients scheduled for surgery will be seen in the preoperative holding area and enrolled in the study if they choose and are appropriate candidates.**

- d. Describe the inclusion/exclusion criteria:

Inclusion Criteria: Patients undergoing total hip arthroplasty under spinal anesthesia. Adults, 18 years of age or older. Patients classified by the American Society of Anesthesiology (ASA) class I, II, or III.

Exclusion Criteria; Any patient not classified as an ASA I, II, or III. Those who are allergic or intolerable to local anesthetics. Patients with pre-existing neurologic or anatomic deficiency and lower extremity on the side of the surgical site, or patients with coexisting coagulopathy. Patients that are pharmacologically anticoagulated will be excluded if placement of peripheral nerve block would be contraindicated according to ASRA (American Society for Regional Anesthesia) guidelines or if spinal anesthesia would be contraindicated according to ASRA guidelines.

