- e. If participants will comprise more than one group or stratification, describe each group (e.g., treatment/intervention, placebo, controls, sham treatment) **and** provide the number of participants anticipated in each group.

Upon enrollment in the study, participants will be randomized 1:1 to either the investigational group (“Quadratus Lumborum Block” group) or the control group (“No Block” group). Participants will be randomized using a random number generator.

- f. Indicate which, if any, of the special populations listed below will be involved in the protocol. Include the Special Populations Review Form (SPRF) if indicated.
- Pregnant Women: Attach [SPRF—Pregnant Women, Fetuses, Neonates/Nonviable Neonates](#)
 - Fetuses: Attach [SPRF—Pregnant Women, Fetuses, Neonates/Nonviable Neonates](#)
 - Neonates/Nonviable Neonates: [SPRF—Pregnant Women, Fetuses, Neonates/Nonviable Neonates](#)

- Prisoners: Attach [SPRF—Prisoners](#)
- Minors (<18 years old): Attach [SPRF—Minors](#)
- Employees or students at institution where research conducted
- Persons who are temporarily decisionally impaired
- Persons who are permanently decisionally impaired
- Non-English Speakers

For each box checked, describe why the group is included and the additional protections provided to protect the rights and welfare of these participants who are vulnerable to coercion: Employees and students are eligible to participate. The suggested language has been included in the informed consent document to fully disclose that this project is separate from the expectations and their relationship with UAB as an employee or student.

g. List any persons other than those directly involved in the protocol who will be at risk. If none, enter "None": **None**

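### Opioid consumption is a primary end point and preoperative opioid users are eligible, but its only planned test is unadjusted, which costs precision

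*Combined protocol and SAP*

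**What the plan says.** - **End point.** Section 14.b opens with "The primary end points are as follows" and lists four items. The second is "Pain medication (opioid) use intraoperatively, as well as at 24 hours and 48 hours postoperatively". No unit is given, and the section does not say whether a patient's usual opioid counts towards the totals.
- **Eligibility (Section 16.d).** The inclusion text begins "Inclusion Criteria: Patients undergoing total hip arthroplasty under spinal anesthesia. Adults, 18 years of age or older" and adds ASA class I to III. The exclusions begin with "Any patient not classified as an ASA I, II, or III", continue with "Those who are allergic or intolerable to local anesthetics", and then cover neurologic or anatomic deficiency on the surgical side, coagulopathy and anticoagulation. Opioid use before surgery appears in neither list.
- **Allocation (Section 16.e).** The text says "participants will be randomized 1:1 to either the investigational group" or to no block, and "Participants will be randomized using a random number generator". No stratification factor is named.
- **Analysis (Statistical Considerations).** The Primary Outcome Analysis paragraph says "Linear regression will be also be used to test the relationship between pain scores and regional anesthetic technique", controlling for clinical and demographic variables that it does not name. No analysis is named for opioid use. What reaches it is the General Data Analysis Plan: a t-test if the data look normal, a Mann-Whitney test if they do not.
- **Sample size.** The 50 per group is justified on the pain score alone.

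**The concern.** A patient who takes opioids before hip replacement can be expected to use more of them afterwards. If usual opioid is counted in the 24 h and 48 h totals, prior use is partly a component of the end point itself. It can be known before randomisation, so it can be used as a covariate without any risk that the block has influenced it.

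The plan uses it nowhere: not in eligibility, not in allocation, and not in the analysis of this end point. The spread between users and non-users then sits in the error term of a two-group comparison with 50 per arm. At stake is a real reduction in opioid use that the trial fails to show, or an estimate that a chance imbalance in users has pushed up or down. Nothing in the sample size paragraph shows that 50 per arm is adequate for opioid use in the first place.

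**Working it through.** **The plan's own figure.** It concerns pain, not opioids. With a difference of 3 and SD 3, the standardised effect is 1. At 50 per group, 1 × √(50/2) = 5, and 5 − 1.96 = 3.04, which gives power of 99.9% against the stated value of about 95%. Power of 95% needs about 26-27 per group. That mismatch is a separate matter. Here it shows only that there is no opioid figure to reproduce.

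**Inputs.** From the documents: 50 per arm, 1:1 allocation, alpha 0.05 (taken as two-sided). Not in the documents, so assumed over a range: the proportion p of preoperative users, how much more they consume, the within-group spread, and the block effect.

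**Step 1: loss of precision in standardised units.** If users sit g within-stratum SDs above non-users, the variance of the unadjusted comparison is multiplied by 1 + p(1 − p)g². Take p = 0.30 and an illustrative block effect of 0.5 SD. Adjusted power is Φ(0.5 × 5 − 1.96) = Φ(0.54) = 70.5%.

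| g | Variance factor | Effective n per arm | Unadjusted power |
|---|---|---|---|
| 0.5 | 1.05 | 47.5 | 68.3% |
| 1 | 1.21 | 41.3 | 62.3% |
| 2 | 1.84 | 27.2 | 45.3% |

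Over p = 10-40%, unadjusted power is 61-67% at g = 1 and 43-57% at g = 2. At g = 0.5 only 2-6% of the effective sample size is lost.

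**Step 2: chance imbalance.** At p = 0.30 the SD of the between-arm difference in users is √(2 × 0.3 × 0.7 / 50) = 0.092. The exact binomial chance of an imbalance of at least 10 percentage points is 33%; of at least 20 points, 3.8%.

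**Step 3: type I error.** Simulated without conditioning on imbalance, the unadjusted test rejects a true null about 5% of the time (4.8-5.1%). At p = 0.30, given a 10-point imbalance, it is still about 5%. Given a 20-point imbalance it is 12.5% (g = 1) to 25.5% (g = 2).

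**Step 4: power of the test the plan would use.** Opioid totals that mix users and non-users are likely to be right-skewed, which sends them to Mann-Whitney. Simulation with lognormal data, CV 60%, a true 30% reduction, 50 per arm, 15-40% users and 1.5- to 3-fold consumption gives:
- planned Mann-Whitney test: about 57-85%;
- log-scale or rank model with arm and preoperative use: about 86-90%;
- gain over Mann-Whitney: about 2 to 31 points;
- untransformed linear model with the same covariate: from about 2 points worse than Mann-Whitney to 17 points better.

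**Hand check of step 4 on the log scale.** The within-stratum variance is ln(1 + 0.6²) = 0.307 (SD 0.555). The effect is |ln 0.7| = 0.357. Adjusted: 0.357/0.555 × 5 = 3.22, so power is Φ(1.26), about 90%. Unadjusted, the variance gains p(1 − p)(ln k)², where k is the consumption ratio:
- 15% users, k = 1.5: 0.307 + 0.021 = 0.328, SD 0.573, power about 88%;
- 40% users, k = 3: 0.307 + 0.290 = 0.597, SD 0.773, power about 64%.

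These lie close to, and slightly above, the ends of the simulated Mann-Whitney range, as expected for a rough approximation.

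**The case against.** The strongest reply is that randomisation already deals with this. A reader might infer that preoperative opioid use could mimic a block effect or bias the comparison. The documents do not support that: allocation is random and 1:1, so any imbalance is chance, and the unadjusted standard error already contains the user-to-user variance. Chance imbalance and lost power are largely the same variance seen twice, and a seriously misleading imbalance is uncommon. This objection stands, and the point is limited accordingly.

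A reader might also infer that prior use would swamp the block effect. That rests on inputs the documents lack. With 25% users and CV 60%, prior use explains 9% of the raw variance if users consume 1.5 times as much, 23% at 2-fold and 41% at 3-fold. A normal-theory t-test calculation on those inputs gives large gains (54% to 65% at 2-fold, 38% to 57% at 3-fold). It is not the right headline, because skewed data would go to Mann-Whitney, which already does better than those t-test figures: about 77% and 66% in simulation.

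Nor do the documents say that usual opioid counts in the totals; that is an inference. The Case Report Form and eligibility checklist are attachments that are not in the public file, so preoperative use may already be recorded. Even so, the statistical section does not use it.

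Finally, admitting opioid users is a legitimate pragmatic choice, and covariate adjustment captures nearly all the precision that stratification would add. Both are fair. What the objection does not supply is an analysis of opioid use that takes account of a factor known at baseline.

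**Conclusion.** The point holds as a matter of efficiency, not validity. Opioid use is a listed primary end point, users are eligible, and the one adjusted model does not cover it. The unadjusted test keeps its type I error near 5% but gives up precision and leaves the estimate open to chance imbalance.

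The documents do not determine how much. Under the stated assumptions the loss against a suitable adjusted model runs from about 2 power points (few users, 1.5-fold consumption) to about 31 (many users, 3-fold). If users consume only slightly more than others, it hardly matters. The choice of scale matters as well as the covariate: on the raw scale, adjustment may gain little or even do slightly worse than Mann-Whitney. The change is worth making because it is cheap and cannot disadvantage either arm.

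**What to change.** 1. Record preoperative opioid use, yes/no and daily amount, before randomisation. Sections 16.c and 16.h place every patient in the preoperative assessment clinic days to weeks before surgery, so its medication list is the natural source. If the Case Report Form already holds the item, nothing need be added.
2. In the Primary Outcome Analysis paragraph, state that 24 h and 48 h opioid consumption will be analysed on a log or rank scale, with a stated way of handling zero values, in a model containing arm and preoperative opioid use. State the unit of consumption and whether usual opioid is counted.
3. Settle this before the interim analysis planned after 50 patients. If enrolment has begun, pre-specifying the covariate before any comparison by arm still recovers most of the benefit.
4. Stratifying the allocation by yes/no is optional.

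The cost is one extra chart item and slightly more analysis work. No patient is excluded and no treatment changes.
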